## List of Abbreviations

Item	Definition
BE	Barrett's Esophagus
eCRF	Electronic Case Report Form
EAC	Esophageal Adenocarcinoma
EC	Ethics Committee
EGD	Esophagogastroduodenoscopy
EMR	Endoscopic Mucosal Resection
HGD	High grade dysplasia
IMC	Intramucosal Carcinoma
IRB	Institutional Review Board
LGD	Low grade dysplasia
PDT	Photodynamic Therapy
RFA	Radiofrequency Ablation

## Study Summary

Title	Non-Endoscopic Surveillance for Barrett's Esophagus Following Ablative Therapy
Methodology	
This is a cross-sectional study of subjects with dysplastic Barrett's Esophagus (BE) who have undergone successful endoscopic ablation with radiofrequency ablation (RFA), to assess the utility of the Cytosponge assay as a non-endoscopic method for monitoring the post-ablation patient. In addition, we will enroll a small cohort of up to 50 subjects with a current diagnosis of BE to collect pilot data for a larger scale study.
 
Subjects presenting to UNC Hospitals for routine endoscopic examinations for current BE or after successful ablation will be offered enrollment in the study. After informed consent, and the same day as the endoscopic procedure, the subject will undergo administration of the Cytosponge assay and complete a questionnaire. The subject will then undergo routine endoscopic surveillance, using a standard Seattle biopsy surveillance protocol. The Cytosponge will be placed in fixative and shipped to the [name] laboratory for processing according to their established protocols. If the Cytosponge tissue specimen is inadequate, the patient will be recalled for a repeat sponge procedure (not endoscopy) 30 days later. Routine care tissue biopsies will undergo standard processing and H&E staining, with assessment by expert gastrointestinal pathologists. Subjects will be contacted via phone 7 days (+/- 2 days) after Cytosponge administration to complete additional questionnaires.

Study Duration	5 Years
Study Center(s)	University of North Carolina, Chapel Hill, NC
Objectives	
Primary objective: To assess the acceptability of a novel, minimally invasive esophageal mucosal sampling technique, the Cytosponge, in subjects undergoing surveillance after radiofrequency ablation. Based on previous data, we hypothesize that the sponge-based sampling technique will be associated with low levels of patient distress, and will be preferred by patients, when compared to standard sedated upper endoscopy, for surveillance of their esophageal mucosa.
 
Secondary objective: To assess the operating characteristics of this technique against a gold standard of upper endoscopy with biopsies for endoscopic surveillance in subjects with a history of successful radiofrequency ablation for dysplastic BE. We hypothesize that the assay will demonstrate both a sensitivity and specificity of >90% in the detection of recurrent BE following radiofrequency ablation. Further, we expect higher accuracy in those with a larger burden of recurrent disease.

Number of Subjects	374 (324 Post-ablation, 50 BE)

Diagnosis and Main Inclusion Criteria	
Inclusion Criteria:
 

1. Male or female subjects, age 18-80 years,

2. Meets the following:

2.1. Previous diagnosis of BE with dysplastic LGD or HGD, as evidenced by both classical endoscopic appearance of salmon-colored mucosa in the tubular esophagus, as well as endoscopic biopsies from the involved areas demonstrating columnar metaplasia with goblet cells. The diagnosis of dysplasia must have been confirmed by a second expert pathologist. Previous EMR of focal nodular HGD or superficial intramucosal cancer (IMC) is allowable, as long as the EMR specimen shows complete resection of any IMC with clear margins, and biopsies following ablation confirm excision of the lesion, AND

2.1.1.A history of complete eradication of both dysplasia and intestinal metaplasia by radiofrequency ablation. Complete eradication is defined as a normal endoscopic appearance of the tubular esophagus, and histologic confirmation by biopsies in 4 quadrants every cm from throughout the length of the previous BE (post-RFA cohort).OR

2.2. Current diagnosis of BE, presenting for routine care endoscopy (BE cohort).

3. Good general health, with no severely debilitating diseases, active malignancy, or condition that would interfere with study participation.

 
Exclusion Criteria:
 

1. Current use of blood thinners such as coumadin, warfarin, clopidogrel, heparin and/or low molecular weight heparin (requires discontinuation of medication 7 days prior to and 7 days after esophagogastroduodenoscopy [EGD] and Cytosponge administration, aspirin use is OK).

2. Known bleeding disorder

3. For the post-RFA cohort, prior ablative therapy of the esophagus other than radiofrequency ablation (RFA), including photodynamic therapy (PDT), more than one session of spray cryotherapy, and any other ablation therapies is exclusionary. However, prior endoscopic mucosal resection (EMR) is acceptable and up to two prior treatments of thermal/coagulation therapy (other than RFA) for focal residual disease following otherwise successful RFA therapy is acceptable. The BE cohort must be treatment naive and have no history of ablation, but prior EMR is acceptable.

4. History of esophageal stricture precluding passage of the endoscope or sponge,

5. Pregnancy, or planned pregnancy during the course of the study,

6. Any history of esophageal varices, liver impairment of moderate or worse severity (Child's- Pugh class B & C) or evidence of varices noted on any past endoscopy,

7. Any history of esophageal surgery, except for uncomplicated fundoplication, and,

8. History of coagulopathy, with INR>1.3 and/or platelet count of <75,000.

9. Planned ablation therapy within 3 days of Cytosponge administration (endoscopic mucosal resection and submucosal dissection is OK).

---------------------------------------	---

Statistical Methodology	
For the primary objective, to assess the acceptability of the novel mucosal sampling technique in subjects after successful ablation, we will assess the distribution of Impact of Events Scale scores, and the intrusiveness and avoidance subscales. We will generate measures of central tendency and distribution of these data. Bivariate analysis will be performed to assess for predictors of low tolerance of Cytosponge surveillance, and a logistic regression model created to assess these factors while controlling for potential confounders. Data will be compared to population norms using parametric statistics. VAS scores will be calculated, and measures of central tendency and distribution reported.
 
Subjects' preferences for Cytosponge vs. endoscopic surveillance, as well as willingness to undergo the procedure again, will be measured as proportions, with bivariate and multivariate analyses for predictors of preference performed.
 
For the secondary objective, to assess the operating characteristics of Cytosponge against a gold standard of upper endoscopy, initially 2x2 tables will be constructed demonstrating Cytosponge and the gold standard findings (Y/N for BE). Sensitivity, specificity, positive predictive value, negative predictive value and accuracy will be calculated. Because Cytosponge positivity may vary based on the burden of BE, we will perform sensitivity analyses, defining "positive" cases as those with recurrent BE of <math>\geq 1</math> cm in length, and then <math>\geq 2</math> cm in length, to assess impact of disease burden on operating characteristics. Multivariate models controlling for age, sex, period of time from last ablation, burden of residual disease, and other potential confounders will be constructed, to assess the impact of these factors on test accuracy. Although we do not expect to see an association between the degree of dysplasia and Cytosponge positivity, exploratory analyses will be performed using degree of dysplasia as a predictor variable, and Cytosponge positivity as the outcome variable.

-------------------------	--

## 1 Introduction

This document is a protocol for a human research study. The study will be conducted in accordance with the International Conference on Harmonisation guidelines for Good Clinical Practice (ICH E6), the Code of Federal Regulations on the Protection of Human Subjects (45 CFR Part 46), and applicable federal regulations and institutional policies. All personnel involved in the conduct of this study have completed human subjects protection training..

### 1.1 Background

Barrett's esophagus (BE) is a premalignant condition associated with the development of esophageal adenocarcinoma (EAC). BE is an extremely common condition, and 1-2% of the general adult population harbor this lesion. In the majority of such subjects, the condition will be indolent, and EAC will not develop. However, in <5% of these subjects, BE will progress to EAC. If BE does progress, it is thought to do so through worsening degrees of dysplasia, from no dysplasia, to low-grade dysplasia (LGD), to high-grade dysplasia (HGD) and on to EAC. The prognosis of EAC is dismal, with a <15% five year survival. For that reason, endoscopic intervention is suggested in the setting of dysplastic BE to avert the development of cancer.

Radiofrequency ablation (RFA) is a safe and effective method for inducing reversion of BE to neosquamous epithelium. RFA is associated with a >90% risk reduction of EAC in the setting of dysplastic BE. However, BE recurs in as many as a quarter of subjects by 36 months following successful RFA. For this reason, surveillance endoscopy is recommended following RFA with complete eradication of intestinal metaplasia. Because this surveillance endoscopy is performed at frequent intervals (every 3-12 months), these procedures obligate the patient to recurrent risks associated with sedation and upper endoscopy, and the inconvenience of these exams. Importantly, the costs associated with this effort greatly impact the cost-effectiveness of RFA treatment.

A minimally-invasive, sponge-based technique for sampling the esophageal mucosa, the Cytosponge, has recently been described. This simple device is comprised of an abrasive sponge encapsulated in a gelatin coating, which is attached to a string. The subject ingests the capsule, which dissolves after a short exposure to gastric secretions. The sponge, now freed from the capsule, is drawn back through the hiatus and distal esophagus and out of the mouth by the string, sampling cardiac and esophageal epithelium. The resulting sample is immunostained for trefoil factor 3, a marker both sensitive and specific for the presence of BE. Preliminary work from collaborators in the U.K. demonstrates high sensitivity and specificity of this assay for detecting BE.

This is a comparative effectiveness study to assess the utility of this technique in endoscopic surveillance of patients with BE following successful RFA. The central hypothesis of this work is that this novel surveillance tool could supplant upper endoscopy in subjects having undergone RFA for BE, providing less invasive and more cost-effective surveillance of this large and growing patient population.

## 1.2 Rationale

*Esophageal adenocarcinoma is a lethal cancer with a rapidly increasing incidence.* In stark contrast to recent progress in other solid tumors, incidence and death rates from esophageal adenocarcinoma continue to rise rapidly in the U.S. There has been a 500% increase in the incidence of esophageal adenocarcinoma (EAC) from the 1970's to the 1990's, and a near-parallel increase in mortality (Figure 1), underscoring the need for more effective prevention and treatment for this lethal cancer. Esophageal adenocarcinoma is thought to develop through a series of metaplastic, then dysplastic, changes of the mucosa. Chronic gastroesophageal reflux (GERD) precipitates a metaplastic change from the normal squamous epithelium, to a more acid-resistant columnar histology. When this columnar epithelium contains goblet cells, it is termed specialized or intestinalized metaplasia. When endoscopically evident, columnar metaplasia with goblet cells in the esophagus is termed Barrett's esophagus (BE).

[figure not shown]

Figure 1 Incidence (top curve) and mortality (lower) from esophageal adenocarcinoma

*Barrett's esophagus is the strongest risk factor for esophageal adenocarcinoma.* BE is associated with a risk of esophageal adenocarcinoma that is 40-120 times that of the general population. Furthermore, BE is an extremely common condition, present in approximately 10% of subjects with chronic GERD, and 1-2% of the general population. Since 10- 20% of adult Americans have at least weekly symptoms of GERD, the number of cases of BE in the U.S. is thought to be >2 million. BE does not generally spontaneously regress; barring an intervention, the patient will have BE for life. Most subjects harboring BE will not progress to EAC. However, in a proportion (0.2-0.5%/year), the metaplastic tissue will progress from low-grade dysplasia (LGD) to high-grade dysplasia (HGD), culminating in EAC. Given the poor prognosis of cancer diagnosed symptomatically, current effort is directed toward early detection and treatment. Current strategies for prevention of EAC focus on endoscopic screening and surveillance. In the approach most commonly used in the U.S., subjects with chronic heartburn are offered a screening endoscopy to assess for BE. Patients found to have BE are then enrolled in endoscopic surveillance, consisting of periodic endoscopy at intervals governed by the presence of dysplasia. In current American College of Gastroenterology guidelines, subjects with BE and no dysplasia undergo endoscopy every 3 yrs. Subjects with BE and LGD have endoscopy yearly. Subjects with BE and HGD are effectively managed with endoscopic therapy, but may also opt for esophagectomy or continued surveillance. Endoscopic exams for GERD and BE are common and costly,

with over 330,000 exams/year in Medicare patients alone, and an average total cost in ambulatory care centers of >\$2,000/exam, making for \$660M in endoscopy costs in the Medicare population alone annually.

*Endoscopic ablation induces reversion of Barrett's Esophagus and decreases progression of disease.* Due to the increasing incidence of EAC and the poor prognosis once cancer has developed, endoscopic ablative therapies are commonly employed in subjects with dysplastic BE. In the most commonly used approach, radiofrequency ablation (RFA), high radiofrequency waves, are delivered by an endoscopic balloon covered with an electrode array, to cause epithelial destruction (Figure 2). Because of the regular spacing of the electrodes, and the delivery of a pre-set amount of energy, the depth of injury is well-controlled and reproducible. Data from our center and others demonstrates that RFA is highly effective in inducing reversion to squamous epithelium in subjects with dysplastic BE. Additionally, data suggest that subjects with dysplastic BE who have undergone ablative therapy with RFA are less likely to progress to either more severe dysplasia or adenocarcinoma. For these reasons, the newest societal guidelines recommend endoscopic ablative therapy for subjects with HGD. Further, RFA is cited as a preferred endoscopic ablative therapy for these subjects. Not surprisingly, RFA has become the predominant method for ablation of BE in the U.S., and to date, over 100,000 of these procedures have been performed in the U.S. (personal communication, [name], CMO, GI Solutions).

[figure not shown]

Figure 2 Circumferential Ablation Catheter

*Recurrence of BE following ablative therapy.* Early enthusiasm for endoscopic ablative therapy was stoked by the hope that, in addition to being an effective anti-neoplastic measure, successful ablation might allow elimination of surveillance upper endoscopy afterward. Because periodic upper endoscopy is used frequently in these subjects (every 3-12 months, depending on the baseline degree of dysplasia), omission of these examinations would result in substantial healthcare savings, and would reduce risk and inconvenience to patients. Unfortunately, data demonstrate a risk of recurrence of BE following successful eradication. Recent data published by the candidate and colleagues from the AIM Dysplasia study demonstrate that approximately 25% of subjects who experience successful eradication of dysplastic BE will develop recurrent BE, almost all in the first year following successful therapy (Figure 3). While most of these recurrences are non-dysplastic BE, dysplastic BE and even adenocarcinoma have been noted to occur after endoscopic ablative therapy. Therefore, following successful endoscopic ablation, patients receive ongoing endoscopic surveillance. Current post ablation surveillance practices are governed by expert opinion, but reported intervals are frequent (every 3-12 months), and involve a copious number of biopsies. The cost and frequency of these examinations impacts the cost-effectiveness of ablative therapy for BE. Additionally, each of these examinations imparts a small, but real risk to the patient. There is substantial inconvenience and negative impact in quality of life associated with enrollment in endoscopic surveillance programs, especially since the center performing the ablation may be far removed from the patient's home, and because currently most exams are done

[figure not shown]

Figure 3 Durability of Eradication of IM

under sedation, requiring both a day missed from work and an accompanying driver for transportation home. Because the number of subjects having undergone RFA in the U.S is now large, and continuing to rise, this is a substantial and growing healthcare cost.

*A novel non-endoscopic technique as a potential surveillance tool after successful endoscopic ablation.* Given the large number of patients with chronic GERD and BE, and the expense and inconvenience of endoscopic examinations for BE, investigators have sought less expensive, non-endoscopic modalities of assessing patients for BE. Early attempts using a non-endoscopic balloon demonstrated inadequate sensitivity, in part due to inadequate cytological samples. More recently, a simple, non-endoscopic device, termed the Cytosponge, has been developed for endoscopic screening of subjects at risk for BE by investigators at the University of Cambridge in the U.K. The Cytosponge is an ingestible gelatin capsule enclosing a compressed spherical mesh of 3 cm diameter, the center of which is attached to a string (Figure 4). The capsule and string are swallowed with water. The string is held at the mouth without tension, allowing the capsule to move into the stomach. After 5 minutes (during which the gelatin capsule dissolves and the sponge is liberated), the sponge is withdrawn by gentle traction on the string. The sponge is placed in fixative for 48 hours, then the cells are pelleted, and processed into paraffin blocks. The pellets are immunostained with trefoil factor 3, which is interpreted simply as either positive or negative by the presence of any staining. In a recent study of 504 subjects with chronic GERD symptoms in the U.K. who underwent both Cytosponge analysis and upper endoscopy, the Cytosponge demonstrated a sensitivity of 90% and a specificity of 94% for the detection of BE (Prague classification C2 or more). Follow-up work with an additional 334 subjects (186 controls, 148 BE) demonstrated similar results, with a sensitivity of 84% and a specificity of 92% (data courtesy of [name], MA(Cantab),MD). These results suggest that the Cytosponge may have suitable operating characteristics to serve as a surveillance tool in subjects with BE or dysplastic BE who have undergone ablative therapy.

Figure 4 Cytosponge

Figure 5 CytospongeTM (left) and Cytosponge I (right) for comparisonCytospongeTM (left) and Cytosponge I (right) for comparison

Medtronic, formerly Covidien GI Solutions, has developed a more refined version of the Cytosponge I (referred hereafter as the Cytosponge™ or "Cytosponge"). The Cytosponge was developed from the Cytosponge I specification and design, with the additional priority of a more reproducible manufacturing process, standardization of dimensions, and other quality related features (Figure 5). Because we seek to assess a tool for widespread clinical usage, this study will use the Cytosponge provided by Covidien GI Solutions (now part of Medtronic).

### 1.3 Device Description

The Cytosponge™ Cell Collection Device (Cytosponge) is intended to collect surface cells from the esophagus. The device consists of a swallowable capsule, which dissolves in the body cavity, releasing a self-expandable sponge. The sponge is then retrieved from the esophagus using an attached cord. During the retrieval process, the sponge collects cells from the most superficial layer of the esophageal mucosa. Once removed from the body cavity, the sponge and cells are retained for investigation and/or testing.

Figure 6 Cytosponge with planned packaging and retrieval cord

The Cytosponge™ Cell Collection Device (Cytosponge) received 510(k) clearance from the FDA on November 26, 2014 (K142695). The Cytosponge™ Cell Collection device is a Class II product under 21 CFR 874.4710 esophagoscope (flexible or rigid) and accessories. This study uses the Cytosponge in accordance with its labeling and is therefore exempt from an IDE per 21CFR812.2.

#### 1.3.1 Prior Utilization

[name] and colleagues administered Cytosponge to 504 patients in a primary care setting and found it to be safe and well-tolerated. Of these patients, 501 (99%) were able to successfully swallow the capsule. Unsurprisingly, given pill-swallowing difficulty in the general population, 3 patients were unable to swallow

the pill, feeling it was too large. No adverse events were noted, and patients demonstrated a low level of anxiety associated with the test. These 504 administrations are documented in a report in the British Medical Journal. These investigators have, since this investigation, administered the Cytosponge to an additional 831 patients as part of the BEST2 study (a multicenter, prospective study to determine whether BE patients can be risk stratified using the Cytosponge) and an interim data analysis shows similarly excellent safety and tolerance profile, with no adverse events reported. Overall, to date, there have been 1,335 documented administrations of the sponge, with no adverse events. Several hundred additional uses of the device have occurred in Cambridge, UK, without adverse event (personal communication, [name]), but have not yet been reported in the peer-reviewed literature.

Cytosponge is extremely similar to Cytosponge I. Although no complications have been reported with this device, there are several theoretical risks associated with the administration of this device. There is the possibility of aspiration whenever instrumentation of the esophagus or stomach is performed. Because the device does not render the upper esophageal sphincter incompetent, this risk is expected to be minimal. Additionally, although the sponge is soft and non-abrasive, subjects could bleed from any mucosal surfaces of the mouth, stomach or esophagus which come in contact with it, and/or experience a sore or irritated throat following administration. Finally, to date there have been >1,000 administrations and detachment of the sponge from the string has occurred in less than 1% of cases. Should the sponge detach from the string, it will be retrieved during the routine care upper endoscopy immediately following administration.

The current study has been designed to minimize occurrence of these theoretical risks. Specifically we plan to exclude those patients who:

- Are unable to discontinue clopidogrel, and/or warfarin for 7 days prior and 7 days after procedure,
- Have a history of esophageal stricture,
- Have any history of esophageal varices, liver impairment of moderate or worse severity (Child's-Pugh class B & C), or evidence of varices noted on any past endoscopy,
- Have any history of esophageal surgery (except uncomplicated fundoplication), and history of coagulopathy, with INR >1.3 and/or platelet count of <75,000.

Importantly, all patients enrolled in this study will have previously and recently received an upper endoscopy during which absence of findings putting the subject at higher risk for these theoretical concerns (conditions such as varices and stricture) will be documented.

Cytosponge administration will occur after an overnight fast to minimize the possibility of aspiration of any gastric contents. Every administered sponge will be assessed post-procedure for signs of fracture or incomplete retrieval of the sponge. In the unlikely case of incomplete retrieval, the sponge will be retrieved with a Roth net at the standard of care endoscopy which will routinely immediately follow the administration of the sponge per the study protocol. Any bleeding noted, either clinically following the sponge administration or due to blood on the sponge itself, will be similarly investigated, and, as necessary, treated during the subsequent endoscopy. Because study inclusion/exclusion criteria are designed to exclude those at highest risk for a bleeding complication, the risk of bleeding in this study should be extremely low.

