### **4.2 Exclusion Criteria**

1. Current use of blood thinners such as coumadin, warfarin, clopidogrel, heparin and/or low molecular weight heparin (requires discontinuation of medication 7 days prior to and 7 days after esophagogastroduodenoscopy [EGD] and Cytosponge administration, aspirin use is OK).
2. Known bleeding disorder
3. For the post-RFA cohort, prior ablative therapy of the esophagus other than radiofrequency ablation (RFA), including photodynamic therapy (PDT), more than one session of spray cryotherapy, and any other ablation therapies is exclusionary. However, prior endoscopic mucosal resection (EMR) is acceptable and up to two prior treatments of thermal/coagulation therapy (other than RFA) for focal residual disease following otherwise successful RFA therapy is acceptable. The BE cohort must be treatment naive and have no history of ablation, but prior EMR is acceptable.
4. History of esophageal stricture precluding passage of the endoscope or sponge,
5. Pregnancy, or planned pregnancy during the course of the study,
6. Any history of esophageal varices, liver impairment of moderate or worse severity (Child's- Pugh class B & C) or evidence of varices noted on any past endoscopy,
7. Any history of esophageal surgery, except for uncomplicated fundoplication, and,
8. History of coagulopathy, with INR>1.3 and/or platelet count of <75,000.
9. Planned ablation therapy within 3 days of Cytosponge administration (endoscopic mucosal resection and submucosal dissection is OK).

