### **5.1.2 Consenting Procedure**

If a subject is screened eligible and interested in the study, the subject will be consented on the study prior to any study procedure. Written informed consent will be obtained by qualified study personnel. Documentation of the consent process will be maintained in the subject's research record.

Subjects will be given ample time to review the consent document and ask any questions they may have. A copy of the written consent form will be provided to the subject and the original maintained in the subject's research record.

If subjects meet all inclusion and none of the exclusion criteria and consent to the study, they will be enrolled in the study. Subjects will be assigned a unique subject code. Each institution will be provided a list of subject codes to use.

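### The risk section and the eligibility criteria state two different stricture exclusions, and the criteria that decide enrolment give the narrower protection.

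*Combined protocol and SAP*

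**What the plan says.** Section 1.3.1 describes the theoretical risks of swallowing the device and then says how the study limits them: "The current study has been designed to minimize occurrence of these theoretical risks. Specifically we plan to exclude those patients who". The stricture item in that list is "Have a history of esophageal stricture", with nothing added about severity or about whether instruments can pass.

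Exclusion criterion 4 in section 4.2 reads "History of esophageal stricture precluding passage of the endoscope or sponge". The Study Summary has the same words.

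Section 5.1.2 says which text governs: "If subjects meet all inclusion and none of the exclusion criteria and consent to the study, they will be enrolled in the study".

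After its list, section 1.3.1 adds a further assurance about all enrolled patients. They "will have previously and recently received an upper endoscopy during which absence of findings putting the subject at higher risk" is established, with stricture and varices given as the examples of such findings. The inclusion and exclusion criteria in section 4 contain no matching item on stricture and set no time limit on a previous endoscopy.

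**The concern.** The two stricture rules admit different patients. Under section 1.3.1 the history alone excludes. Under criterion 4 the history excludes only if the stricture stops the endoscope or the sponge. Someone with a stricture that can be passed falls between the two, and the risk section describes that person as not in the study.

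This bears on safety because section 1.3.1 is where the protocol argues that the residual device risk is small, and part of that argument is an exclusion broader than the one applied. The same-day endoscopy cannot make up the difference. Sections 3.1 and 5.1 put the sponge first and the endoscopy after it, so a stricture seen at that endoscopy is seen after the first administration.

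**Working it through.** No arithmetic applies. The plan states no figure on this point, and the check is a comparison of texts.

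**Step 1: who is treated differently.**

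| Patient | Section 1.3.1 list | Criterion 4 (Summary and 4.2) |
|---|---|---|
| No history of stricture | not excluded | not excluded |
| Stricture that stops the endoscope or sponge | excluded | excluded |
| Current stricture that both can pass | excluded | **eligible** |
| Past stricture, now resolved, that never stopped either | excluded | **eligible** |

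The texts disagree in the last two rows. Section 5.1.2 settles the practical outcome in favour of the right-hand column.

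**Step 2: is section 1.3.1 simply a loose paraphrase?** Its list against section 4.2, item by item:

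- Varices and liver impairment: "Have any history of esophageal varices, liver impairment of moderate or worse severity" has the same limits as criterion 6.
- Esophageal surgery: same limits, including the exception for uncomplicated fundoplication.
- Coagulopathy: same INR and platelet limits.
- Blood thinners: 1.3.1 names clopidogrel and warfarin. Criterion 1 also names heparin and low molecular weight heparin.
- Known bleeding disorder: criterion 2, absent from the 1.3.1 list.
- Stricture: 1.3.1 is broader than criterion 4.

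The list is therefore not a faithful copy throughout. In the blood-thinner and bleeding-disorder items, however, the criteria exclude more than the risk section says. Stricture is the item where the risk section promises more than the criteria deliver.

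**Step 3: does the endoscopy assurance close the gap?** Section 1.3.1 says that absence of "conditions such as varices and stricture) will be documented" at an earlier, recent endoscopy. Three observations:

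- It could bear on a current stricture but not on a resolved one, so it would not reach the last row of the table.
- If criterion 4 admits a patient with a current stricture that can be passed, the assurance need not be true of every enrolled patient.
- It is only partly carried into section 4. Criterion 6 excludes varices seen on any past endoscopy. Inclusion 2.1.1 requires, for the post-ablation cohort, an earlier endoscopy at which the tubular esophagus looked normal. Neither sets a date limit, and neither is a check for stricture at study entry.

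**Step 4: where recency is in doubt.** Sections 1.1 and 1.2 give post-ablation surveillance intervals of 3 to 12 months, so those patients will usually have had a fairly recent examination. Entry to the BE cohort under inclusion 2.2 needs only a current diagnosis and a routine endoscopy appointment. For part of that group the protocol's own background gives a long interval: "subjects with BE and no dysplasia undergo endoscopy every 3 yrs". The recency gap therefore falls mainly on a cohort of up to 50 out of 374 planned subjects. The stricture mismatch in Step 1 applies to both cohorts.

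**The case against.** The strongest reply is that the operative rule is not in doubt. The Summary and section 4.2 agree word for word, section 5.1.2 enrols by the criteria, and the outlier is one bullet in an introductory section that departs from section 4.2 elsewhere too. On that view this is drafting shorthand. Much of this stands: a coordinator who follows section 4.2 has one clear rule. It does not remove the contradiction. The bullet is offered as a specific risk-control measure, no text says that section 4.2 overrides it, and the departure is towards overstating the protection.

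Several stronger readings are tempting, and the documents do not support them:

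- *That the stricture protection is not in force.* Strictures that stop the endoscope or sponge remain excluded.
- *That the ethics committee is shown only the broader rule.* Section 10 sends it the protocol, which contains both wordings.
- *That a count of affected patients can be given.* The documents contain no stricture rate, and any assumed rate applied to the 324 post-ablation subjects would rest on the assumption alone.
- *That the acceptability or accuracy results are distorted.* No mechanism is described by which a stricture that can be passed would bias either.
- *That no criterion concerns previous endoscopy.* Criterion 6 and inclusion 2.1.1 do. What is missing is recency and a stricture check.
- *That the 3-year interval is a study interval.* It is guideline background for non-dysplastic BE.

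**Conclusion.** The point holds as an internal contradiction on a device-safety criterion. The protocol describes one stricture exclusion and applies a narrower one, and patients with a stricture that can be passed are classified differently by the two texts. The claim of a recent endoscopy documenting absence of stricture is likewise not secured by section 4, with the recency part confined mainly to the BE cohort.

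The size cannot be expressed as a number of patients. The conclusion rests on the plain wording of sections 1.3.1, 4.2 and 5.1.2 and the Summary, and on no assumed rate. It should be corrected because it concerns a stated safety protection and is cheap to correct. It does not threaten the validity of the study's estimates.

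**What to change.** Reconcile section 1.3.1, section 4.2 and the Study Summary so that all three carry a single stricture criterion. Reconcile the statement in 1.3.1 about an earlier, recent endoscopy with section 4: either make it an eligibility check with recency defined, or reword it to claim only what the criteria secure. The choice of rule is a clinical matter for the sponsor and investigators, and this review takes no position on it.

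The cost is a wording amendment with the usual ethics submission. If the broader stricture text is kept, some otherwise eligible subjects are lost, in a number the documents do not allow one to estimate. If the narrower text is kept, the risk argument in 1.3.1 has to be restated to match. Sample size and analysis methods need no change in wording under either choice.
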